******MAIN RESEARCH QUESTIONS, STUDY AIMS, SPECIFIC HYPOTHESES******

1.1 Please clearly state your overall research questions and/or study aims.

Primary Outcome:

- 1) Is a fixed dose of 4-factor prothrombin complex concentrate (4FPCC) comparable to FDA-approved variable dosing for reversal of warfarin-induced anticoagulation (defined as an international normalized ratio [INR] ≤ 1.5) in patients with an INR ≥ 2 experiencing an emergent bleed or requiring emergent surgery?

Hypothesis: A fixed dose of 4FPCC will be comparable to FDA-approved variable dosing for reversal of warfarin-induced anticoagulation (defined as an international normalized ratio [INR] ≤ 1.5) in patients with an INR ≥ 2 experiencing an emergent bleed or requiring emergent surgery.

Secondary Outcomes:

- 1) What is the incidence of a thromboembolic event occurring within 7 days post-reversal with a fixed dose as compared to FDA-approved variable dosing of 4FPCC?

Hypothesis: The occurrence of a thromboembolic event within 7 days post-administration of a fixed dose of 4FPCC is lower than that of the FDA-approved variable dosing.

- 2) Does a fixed dose of 4FPCC provide significant cost-savings to the institution in dollars when compared to FDA-approved variable dosing?

Hypothesis: Utilizing a fixed dose of 4FPCC will provide for significant cost-savings to the institution as compared to FDA-approved variable dosing.

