The ED research interns and CCRC research staff will be utilized to identify eligible patients. When a patient presents with an emergent bleed or requiring emergent surgery and is on chronic warfarin anticoagulation requiring 4FPCC use, the physician will notify the ED research intern or CCRC staff. The ED research intern or CCRC researcher will determine eligibility and review inclusion and exclusion criteria with the treating physician. In addition, the CCRC intern is always in the emergency department and may notice a potentially eligible patient on the ED Track Board in EPIC. The intern would then notify the physician if he or she were not already aware of the patient. If a patient is determined to be eligible and the physician approves enrollment into the study, the CCRC intern will immediately proceed with randomization. Once the patient is randomized, the physician will be notified of the dosing order from the randomization and the physician will place the appropriate order. Due to the emergent nature of this condition, randomization envelopes will be in a locked area in the Emergency Department in order to expedite randomization and not impede urgent treatment.

Following randomization, the patient will either receive either a fixed or variable dose of 4FPCC per study protocol.

CCRC interns will abstract the study data points from the patient's EMR while the patient is in the Emergency Department

and again at the time of discharge. The variables listed on the attached data collection form will be incorporated into a secure RedCap database that the interns will use to enter the data. All patients will be identified in RedCap with a study ID number that is not linked to identifying information in the database.

Randomization

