Given the emergent nature of need for care with this clinical population, randomization will need to happen quickly following the physician decision to use 4FPCC for bleeding reversal. The CCRC intern is in the emergency department 24/7 and is able to respond quickly to the needs of patients upon physician request. This study will utilize a permuted block randomization schedule to allow for equal allocation of subjects in each arm. Given that we expect to enroll 4 patients per month over a 1-year time period, allowing for a total sample size of 48 patients (24 per group), the randomization scheme will consist of 12 permuted blocks of four. Sealed envelopes with the dosing arm (fixed vs. weight-based) will be in the research file in the locked medication room located in Pod E. Pod E is the area of the emergency department reserved for the most acute patients and is where these patients will be treated. All interns have badge access to the medication room. A filing box containing documents specific to ED research is located in the medication room. Once the treating physician deems a patient eligible, the intern will retrieve the envelope from the medication room; open the envelope and the physician will enter the order. We do not anticipate that randomization will take more than 20-30 seconds and thus will not delay patient care or treatment.

Staff Training

CCRC Intern Group

[name] will train the CCRC intern group at the monthly intern dinner in January 2016. Training will involve a PowerPoint presentation reviewing the background and significance of this study as well as the aims and hypotheses. The interns will be trained on the full study protocol with emphasis on the inclusion and exclusion criteria. [name] will also review a mock patient for data abstraction to ensure that everyone is getting data points in the EMR from the same location. [name] will train interns on the randomization procedure.

ED Staff Training

- All attending physicians will be informed of the study at the monthly ED faculty meeting in January. [name] will lead this presentation and will answer any questions.
- Residents will be informed of the study during the monthly Resident Rounds in January. This is a monthly 4-hour meeting that is mandatory for all ED residents. [name] attends this meeting and will present the study to the residents.

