- ED nursing staff will be informed about the study during daily huddles in the Emergency Department. Huddles are held three times daily for the nursing staff so that all shifts are informed. CCRC staff will attend the huddles to inform nursing staff of the study and answer any questions. We have utilized this method of education in the past and it is the best way in which to reach all nursing staff. We will attend huddles for the two weeks prior to study start.

ED Pharmacy Staff

ED pharmacy staff will be fully trained on the protocol by [name] and [name]. [name] is a senior pharmacist in the emergency department and is the primary investigator on this study. [name] is a PGY-1 Pharmacy Resident at Regions Hospital and is a Co-Investigator on this study. Both [name] and [name] will participate in training the pharmacy group.

2.7 Describe any interventions that are used in this study.

	Not Applicable
--	----------------

Eligible patients will be randomized in a 1:1 fashion to receive either a fixed dose of 1500 IU or the FDA-approved variable dosing based on body weight and presenting INR. The FDA-approved variable dosing algorithm is as follows: initial INR 2-3.9: 25 IU/kg (maximum dose 2500 IU), initial INR 4-6: 35 IU/kg (maximum dose 3500 IU), and initial INR >6: 50 IU/kg (maximum dose 5000 IU). The patient weight will be obtained using a scale and documented by the treating RN.

Randomization will be initiated with the research team member notifying the attending physician of patient enrollment, and the physician placing the order that is immediately visible in EPIC to the IV pharmacist preparing the medication. The pharmacist will prepare the study medication as either the fixed or variable dose. Exact doses of 4FPCC administered may vary slightly from the calculated doses as the amount of 4FPCC differs based on the vials utilized. The doses are unable to be blinded by the research team, as the fixed dose will have less drug volume.

Following the randomization to study doses, the patient will be monitored for continued bleeding by the treating physician. If the patient receiving the 1500 IU fixed dose remains in a bleeding state and the INR remains above goal, an additional 500 IU may be administered at the physician's discretion to minimize bleeding and attempt to achieve hemostasis. If a

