patient does receive the additional 500 IU dose, the patient will be included in the intent-to-treat (ITT) analysis and considered a treatment failure for fixed dosing. (NOTE: this should be based on INR – not subjective assessment of bleeding)

All patients on chronic anticoagulation with warfarin who present with an emergent bleed or need for urgent surgery will obtain an initial INR value via the iSTAT point of care test and a laboratory INR. Due to urgent need for administration of 4FPCC, the laboratory INR may not be evaluated prior to randomization. After patient enrollment and randomization, the patient will receive the study medication and have a laboratory INR drawn 15 minutes post-administration. Obtaining a pre- and post-INR laboratory value is standard of care in the emergency department. The laboratory INRs will be utilized in all cases to evaluate the change in INR from pre- to post-administration of 4FPCC. The INRs will be collected and documented in the EMR by the treating RN. All patients enrolled in the study will be evaluated and identified via the EMR for development of a thromboembolic event within 7 days post 4FPCC administration. A 7-day follow-up period was chosen based on other studies evaluating a 4FPCC fixed dose [11,12]. Enrolled patients will be prospectively followed throughout admission with daily chart review to determine if a thromboembolic event occurred. The last patient progress note written within the 7-day follow-up period will be evaluated. This will allow us to include all patients who might have been discharged prior to the 7-day period, but were readmitted with a thromboembolic event.

2.8 Provide a brief, sequential, bullet-point description of the all the data collection activities you will conduct from start to finish (e.g., chart review, patient survey, follow-up visits, data pull from the electronic medical record, etc.) and who will conduct each. Please see our [Example of Data Collection Steps](#).

The current study will assess patient data among enrollees for the outcomes presented in section 1.1:

- 1) Treating physician will notify CCRC intern of potential study patient or the intern will notice the patient on the ED Track Board and notify the physician
- 2) Patient identification and inclusion/exclusion screening performed by the ED research intern or CCRC researcher
- 3) Physician approves the enrollment into the study

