2.12 Provide operational definitions of any variables listed above that aren't adequately described by the variable name above, and provide a brief background of any validated measurement scales listed above.

Thromboembolic events may include deep vein thrombosis, pulmonary embolism, ischemic stroke or transient ischemic event, or myocardial infarction.

Indication for 4FPCC may include, but will not be limited to, intracranial hemorrhage, gastrointestinal hemorrhage, ruptured abdominal aortic aneurysm, intrathoracic hemorrhage, spinal cord hemorrhage, neck hematoma, or other emergent surgical indication.

2.13 If you are collecting data elements besides those listed in Table 2.10 above, provide a justification for gathering the additional data.

N/A

Reminder: For chart review studies, a data collection form must be uploaded with your application listing variables collected and how they are recorded (chart review studies). Provided are links to two example chart review tools: [Word Chart Review Example](#) and [Excel Chart Review Example](#)

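### Thromboembolic event review (Aim 2) has no named reviewer and no masking, while the intern group that abstracts the data knows the arm and the expected direction

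*Combined protocol and SAP*

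**What the plan says.** **Blinding.** Section 2.7 states: "The doses are unable to be blinded by the research team, as the fixed dose will have less drug volume". The limitations in 3.9 say only that dosage assignment cannot be blinded. Neither place mentions outcome assessment.

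**Who knows the arm.** Under Randomization in 2.6 the intern fetches the envelope, and the steps are to "open the envelope and the physician will enter the order". The exact dose, any additional dose in the fixed arm and the charge are also study variables (2.8, 2.11), so the arm can be seen in the abstracted data by an intern who did not open that envelope.

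**What the interns are taught.** Their training (2.6) involves "reviewing the background and significance of this study as well as the aims and hypotheses". The first secondary hypothesis in 1.1 has a direction: event occurrence "within 7 days post-administration of a fixed dose of 4FPCC is lower than that of the FDA-approved variable dosing".

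**Who abstracts.** Section 2.6: "CCRC interns will abstract the study data points from the patient's EMR while the patient is in the Emergency Department", and again at discharge.

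**How events are found.** Under 2.7 patients are "prospectively followed throughout admission with daily chart review to determine if a thromboembolic event occurred", and the last progress note within the 7 days is read. No one is named for this review, nor for step 12 of 2.8 (the 7-day evaluation), although 2.8 asks who conducts each activity.

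**What counts.** Section 2.12: "Thromboembolic events may include deep vein thrombosis, pulmonary embolism, ischemic stroke or transient ischemic event, or myocardial infarction". No diagnostic criteria follow.

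**How it is analysed.** Aim 2 in 3.1 reports risks, risk difference, risk ratio, 95% confidence intervals and p-values. It gives no event rate and no decision rule, and says the study is not powered for this outcome.

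**The concern.** Drug volume makes masking impractical at the bedside. The thromboembolic call is a different task. It is made later, from the record, by someone who need not have been at the bedside. The plan does not take up the possibility of masking that person.

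Three features together allow a lean. The group abstracting the data knows the arm. It has been told which direction is expected. The call is made from free-text notes against a list that is open and has no criteria. A reviewer in that position can, without intending to, search one arm harder or resolve a doubtful entry differently.

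At stake is the only clinical event outcome among the stated aims. Section 6.3 says the results will influence whether the hospital adopts fixed dosing, so the estimate will be read even though it is unpowered. The primary endpoint is a laboratory INR and is largely out of reach of this problem.

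**Working it through.** **1. The plan's own power figure.** The documents give one, 22% for the primary analysis (3.8), and none for Aim 2. Inputs: 24 per arm, margin -0.10, reversal 0.77 in both arms, alpha 0.05.

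- Normal approximation: Φ(0.10 / √(2 × 0.77 × 0.23 / 24) − 1.645) = Φ(0.823 − 1.645) = 20.6%.
- Exact binomial enumeration of the same rule: 22.0%.

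The stated figure is reproduced at one-sided 0.05. Masking the event review changes nothing in it.

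**2. Weight of one event.** Arm sizes: 24 (3.8), or 30 if all 60 patients in 3.2 are enrolled 1:1.

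- One reclassified event: 1/24 = 4.2 points; 1/30 = 3.3 points.
- Two, leaning the same way: 2/24 = 8.3 points; 2/30 = 6.7 points.

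**3. What that does to the reported result.** The counts below are assumed, since the plan gives no event rate. They are fixed v variable at 24 per arm, with Fisher's exact p and a Newcombe 95% interval for the risk difference (RD).

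| Counts | RD (points) | Risk ratio | p | 95% CI (points) |
|---|---|---|---|---|
| 2 v 2 | 0.0 | 1.0 | 1.00 | -18.5 to 18.5 |
| 1 v 2 | -4.2 | 0.5 | 1.00 | -22.0 to 13.0 |
| 1 v 3 | -8.3 | 0.33 | 0.61 | -27.2 to 9.7 |
| 0 v 4 | -16.7 | 0 | 0.109 | -35.9 to 0.4 |
| 0 v 5 | -20.8 | 0 | 0.0496 | -40.5 to -2.8 |

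One event missed in the fixed arm and one over-called in the variable arm turns 2 v 2 into 1 v 3. The estimate goes from no difference to a risk ratio of one third, and p stays at 0.61. The same two errors turn 2 v 1 (RD 2/24 − 1/24 = +4.2) into 1 v 2 (RD -4.2), which reverses the sign.

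**4. How often the counts are this close.** Assumed equal event rates of 2% to 10%, independent binomial counts, 24 per arm:

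| Assumed rate | Expected events in 48 | Arms differ by at most 1 | Arms differ by at most 2 | Fisher p < 0.05 |
|---|---|---|---|---|
| 2% | 1.0 | 89% | 98% | 0.01% |
| 5% | 2.4 | 70% | 91% | 0.4% |
| 8% | 3.8 | 59% | 83% | 1.2% |
| 10% | 4.8 | 54% | 78% | 1.7% |

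If the arms differ by at most one event, one reclassification is enough to create a difference or erase it. Across the assumed range that is the situation at least half the time. Significance is another matter: with no events in one arm it takes 5 in the other at 24 per arm, and 6 at 30 per arm (p = 0.024).

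**The case against.** The strongest reply has four parts.

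**The plan does not say that interns judge the events.** This stands. A reader might infer that the very intern who opened a patient's envelope later decides whether that patient had an event. Section 2.6 gives interns abstraction in the ED and at discharge. The daily review and step 12 of 2.8 name nobody, and the interns are a pool. That the group does this work is a reasonable inference, not a statement in the text. The data collection form that 2.6 mentions is not in the text reviewed and may say more.

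**The volume sentence is about the doses.** This stands too. A reader might take it as the sponsor's reason for leaving outcome review unmasked, but the plan offers no reason. It is silent on the matter, and that silence is the point.

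**Aim 2 is unpowered, so one or two events decide nothing.** This is right about significance, and a reader should not infer that a couple of leaning calls settle Aim 2. An error at the edge, 0 v 4 read as 0 v 5, would cross 0.05, but such lopsided counts are unlikely at the assumed rates. Low power does not answer the bias, however. It describes random error, while a lean is systematic and enters the risk difference and risk ratio that will be reported.

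**Much of the task is copying the treating team's diagnosis, and that team is unmasked.** This is partly right. Masking the abstractor cannot reach decisions about whom to investigate or what the note says. The abstractor still chooses what to search for and what qualifies under an open list. Training on a mock patient helps interns find data in the same place, but does not hide the arm.

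**Conclusion.** The concern holds in limited form. The intern group that abstracts the study data knows the arm and the hoped-for direction. The 7-day thromboembolic review has neither a named reviewer nor masking, and the reason given in 2.7 reaches only administration of the drug. Ascertainment of this secondary outcome can therefore lean toward the stated hypothesis.

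The size is 4.2 points of risk difference per reclassified event at 24 per arm (3.3 at 30). From the small, near-equal counts that the assumed rates imply, this is enough to change the direction and size of the Aim 2 estimate, not its significance.

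The conclusion rests on two assumptions: event rates between 2% and 10%, and interns, or staff who can see the arm, doing the review. The documents give no misclassification rate, so this is an exposure to bias and not a measured one. The only event figure they give, in 1.3, is none within 7 days in a cited fixed-dose cohort.

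**What to change.** In 2.7 and in step 12 of 2.8:

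- Assign the 7-day thromboembolic review to an existing intern or CCRC staff member who did not enrol or randomise that patient. Hypothesis training matters much less once the reviewer does not know the arm.
- Record the outcome on a separate REDCap form that shows no arm, dose, additional-dose or charge field.
- Have the reviewer work first from post-dose diagnoses, imaging and laboratory reports, without opening the medication record. Progress notes are consulted only as needed, for clinical diagnoses such as TIA and for readmissions.
- Record on the form whether the reviewer became aware of the arm.

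In 3.9, state that event ascertainment by the treating team remains unmasked.

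Two stronger measures are not proposed. Physician adjudication on redacted records needs an extra assessor, whom the documents do not show to be on the team. A closed list requiring imaging or laboratory confirmation could exclude the transient ischaemic events that 2.12 lists.

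The cost is one form, a reassignment of existing work and a few minutes per chart. Sample size, alpha and power do not change. Masking will be imperfect, because the medical record and its notes may mention the dose.

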2.10 Describe your plans for ensuring data security

This study involves only minimum necessary data, in which only de-identified data will be reported. Data will be entered and stored in an HP secure RedCap database. All patients in the RedCap database will be identified only by their assigned study ID number. The database linking the patient MRN and ID number will be stored on a password-protected CCRC share drive that is only accessible to CCRC assigned staff. All electronic identifiers will be destroyed from Regions Hospital computers at the time of manuscript completion. There will not be paper data collection records for this study.

2.11. List the KEY variables that will be collected to support the study aims outlined in item 1.1. KEY variables include those used for:

- 1) achieving the study aims (outcomes, predictors, potential confounders),**
- 2) identifying the study population (for inclusion/exclusion criteria),**
- 3) describing the study population**

Please see an [Example of a Completed Table](#) and an [Example Data Dictionary](#).

Variable Name	Data Source (patient survey, EMR, claims, registry)	Purpose (sample identification, description, grouping variable, study endpoint, predictor, covariate)	Measurement Scale (binary, continuous)
Presenting INR (iSTAT and laboratory value)	EMR	Study endpoint	Continuous
Time of initial INR draw (iSTAT and laboratory value)	EMR	Variable	Continuous
INR at 15 minutes post-administration of 4FPCC	EMR	Study endpoint	Continuous
Dose of 4FPCC in IU	EMR	Study endpoint	Binary
Time to administration of 4FPCC in minutes	EMR	Study endpoint	Continuous
Administration of additional 4FPCC in fixed dose arm	EMR	Study endpoint	Binary
Thromboembolic events within 7 days	EMR	Study endpoint	Binary
Timing of thromboembolic event	EMR	Study endpoint	Continuous

Patient charge of 4FPCC in dollars	EMR	Study endpoint	Continuous
Institution cost of 4FPCC in dollars (cost per unit)	Biocare	Study endpoint	Continuous
Weight (kg) at presentation	EMR	Covariate	Continuous
Use of other reversal agents (vitamin K and FFP)	EMR	Covariate	Binary
Age	EMR	Covariate	Continuous
Indication for 4FPCC	EMR	Covariate	Binary
Attending Provider Specialty (i.e. emergency medicine, trauma, hematology/oncology, neurosurgery)	EMR	Covariate	Binary
Hospital unit (i.e. emergency department, SICU, MICU, etc.)	EMR	Covariate	Binary
Eligible patients not enrolled due to physician discretion	EMR	Covariate	Binary

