Based on previous literature [D'Agostino 2003, Goldstein 2015] and the available study sample, we propose to set the non-inferiority margin M to -0.1. In other words, if the proportion of warfarin reversal among fixed dose patients is no worse than 10% less than the proportion of warfarin reversal among variable dosed patients, then we will reject the null hypothesis (superiority of variable dosing), and consider the fixed dose to be acceptably non-inferior to variable dosing.

Results to be reported for this aim will consist of the proportion of reversal for each group, the risk difference (RD; the proportion of reversal in fixed group minus the proportion of reversal in variable group), and the risk ratio (RR; the proportion of reversal in fixed group divided by the proportion of reversal in variable group), along with 95% confidence intervals and p-values as appropriate. Non-inferiority will be established if the lower bound of the RD is greater than the pre-specified margin M (-0.1). The primary analysis will use an intent to treat (ITT) approach (fixed vs. variable treatment assignment); however, we will also conduct supplemental analyses using an 'as treated' or 'per protocol' (PP) approach, in which we will compare patients' actual received dose (regardless of assignment) with respect to successful reversal of anticoagulation. We expect the PP approach to complement the primary ITT results, and will be informative particularly if there is non-trivial overlap in dosing by assignment group.

(Secondary) Aim 2: Fixed vs. variable dose 4FPCC and thromboembolic events

Study patients will be followed for 7 days post-administration of 4FPCC for thromboembolic events, as defined in Section 2.12. For this outcome, we will calculate and report the risk (proportion of patients experiencing an event in each group), RD, and RR, with 95% confidence intervals and p-values, as described in Aim 1. While we expect the risk of thromboembolic events to be lower in the fixed dose group, due to the limited number of anticipated thromboembolic events in the study population, the study will not specifically be powered to detect statistically significant differences by dosing group.

(Secondary) Aim 3: Fixed vs. variable dose 4FPCC and costs

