3.9 What are the limitations of the proposed approach and analysis?

The primary limitation will be low statistical power to reject the null hypothesis (superiority of variable dose 4FPCC), given limited sample size. Additionally, due to the nature of the intervention, blinding of treatment dosage assignment will not be feasible. Finally, patient follow-up for thromboembolic events at 7-days post 4FPCC administration may not be achieved in all patients due to discharge.

3.10 Please name the people who completed the analysis section of this application.

[name], MPH

3.11 Please name the people who will summarize data and conduct statistical analysis.

[name], MPH, and/or another member of the HealthPartners Institute Research Methodology Group.

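### After discharge, 7-day thromboembolic events are sought only through the last in-window progress note in this hospital's EMR, and Aim 2 has no rule for incomplete follow-up

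*Combined protocol and SAP*

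**What the plan says.** **Ascertainment (Section 2.7).** The general commitment is EMR-wide: "All patients enrolled in the study will be evaluated and identified via the EMR for development of a thromboembolic event within 7 days post 4FPCC". During the stay the method is explicit: "Enrolled patients will be prospectively followed throughout admission with daily chart review to determine if a thromboembolic event occurred". The end-of-window check is then "The last patient progress note written within the 7-day follow-up period will be evaluated", with this justification: "This will allow us to include all patients who might have been discharged prior to the 7-day period, but were readmitted with a thromboembolic event".

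**Timing of abstraction.** Section 2.6 has interns abstract data in the ED "and again at the time of discharge". Section 2.8, step 12, lists a 7-day evaluation but gives no method.

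**Variables and sources.** Section 2.11 lists "Thromboembolic events within 7 days" as a binary endpoint taken from the EMR, and separately the timing of an event. It lists no discharge date and no last date of known status. Section 2.13 adds no further data elements. In Section 8.7 only Epic is marked as a data source; state death data and claims are not. Telephone number is unmarked in 8.9, and mortality data is unmarked in 8.10.

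**Analysis (Section 3.1, Aim 2).** "we will calculate and report the risk (proportion of patients experiencing an event in each group"), followed by the risk difference and risk ratio. Nothing is said about patients not observed to day 7.

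**Missing data.** Section 3.5 expects little loss to follow-up because the INR is available within 15 minutes, and names Aim 2 as a possible exception when patients die in hospital. Section 3.9 concedes that "patient follow-up for thromboembolic events at 7-days post 4FPCC administration may not be achieved in all patients due to discharge".

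**The concern.** The assurance in Section 2.7 covers only patients who come back. Someone discharged on day 3 and not seen here again has a last note from day 3 or earlier, and the rest of the window is blank. Taken literally, the progress-note rule also passes over a return visit that leaves only an ED note or an imaging report, and an event with onset on day 7 that is written up on day 8.

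The reason given in Section 3.5 for expecting little loss applies to a 15-minute laboratory value, not to a 7-day clinical outcome. Section 3.9 recognises the gap, but disclosing it does not tell the analyst what to do with the affected patients.

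Thromboembolism is the only safety outcome listed in Section 1.1, and its hypothesis favours the fixed dose. Sections 5.2 and 6.3 say that the results may change hospital policy. With about 24 patients per arm, a low event count could reflect safety or could reflect unobserved days, and the planned report would not let a reader tell which.

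**Working it through.** **No plan figure to reproduce.** The documents give no event rate, length of stay or power for Aim 2. The 22% power in Section 3.8 belongs to Aim 1 and has no bearing here.

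**Step 1: what each route can see.**
- Event during admission: daily chart review. Covered.
- Event after discharge, readmitted here within 7 days with a progress note: covered by the last-note rule.
- Event after discharge, recorded here only in an ED note or imaging report: not covered by the literal last-note rule, though the EMR holds it.
- Onset by day 7, documented here after day 7: not covered by the literal rule, though the EMR holds it.
- Event treated elsewhere or never presented: no stated route.

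The gap is therefore confined to time after discharge.

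**Step 2: bias if unobserved patients count as non-events.** Let r be the true 7-day risk, d the share of all 7-day events that belong to patients discharged before day 7, and m the share of those patients' events that occur after discharge and are never captured. Then

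observed risk = r × (1 − d × m),

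so the relative understatement is d × m, and the expected number of missed events among 48 patients is 48 × r × d × m. All three inputs are assumptions: r = 2%, 5%, 10%; d = 10%, 25%, 50%; m = 25%, 50%, 100%.

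- Smallest relative loss: 0.10 × 0.25 = 2.5%. At r = 2%, missed events = 48 × 0.02 × 0.025 = 0.024.
- Middle: 0.25 × 0.50 = 12.5%. At r = 5%, observed = 0.05 × 0.875 = 4.4%; missed events = 48 × 0.05 × 0.125 = 0.3.
- Largest: 0.50 × 1.00 = 50%. At r = 10%, observed = 5.0%; missed events = 48 × 0.10 × 0.50 = 2.4.

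**Step 3: effect on the comparison.** If d × m is the same in both arms, the risk ratio is unchanged and the risk difference shrinks towards zero by the factor (1 − d × m). If it differs between arms, the bias can go either way.

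**Step 4: does the unstated denominator matter at this size?** Take 24 patients in an arm, 6 of them (assumed) without known 7-day status.
- One event: 1/24 = 4.2%, or 1/18 = 5.6%.
- No events: the exact two-sided 95% upper limit is 1 − 0.025^(1/n), which is 14.2% for n = 24 and 18.5% for n = 18.
- No events seen, but all 6 unknown patients had one: 6/24 = 25%.

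The same data support noticeably different safety statements depending on a choice that the plan leaves open.

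**The case against.** **Stands.** Inpatients have daily chart review, and the opening commitment in Section 2.7 covers the whole EMR. Section 8.10 marks provider notes, diagnoses and procedures as study content, so staff may well look beyond progress notes in practice. Section 2.11 records event timing, which already supports counting by onset. The population is acutely ill, so many patients may still be in hospital on day 7. Aim 2 is secondary and expressly unpowered, and Section 3.9 discloses the limitation.

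**Stronger readings that the documents do not support.**
- A reader might infer that events are sought only in the last note and at discharge. The sentence just before that rule sets daily review throughout the admission.
- A reader might infer that the plan codes early-discharged patients as event-free. That is the natural result of a binary field and a proportion over each group, but no section says it. A binary variable can be left missing, and the data collection form mentioned in Section 2.6 is not among the documents.
- A reader might infer that the comparison is biased towards one arm. The documents give no length of stay by arm and no reason to expect a difference.

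**Does not answer the point.** Neither disclosure nor low power supplies a rule for incomplete windows, and the literal end-of-window rule is narrower than the EMR that it draws on.

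**Conclusion.** The point holds in a limited form. Ascertainment during admission is adequate as described. After discharge it rests on a rule that can miss events even when this hospital's EMR contains them, and Aim 2 has no rule for patients not observed to day 7. The downward bias is conditional on unobserved patients being kept as non-events. Its size is unknown: 2.5% to 50% relative over the assumed inputs, with a middle case of 0.3 missed events among 48 patients. No direction of bias in the arm comparison can be claimed. The primary INR analysis is unaffected. This is an inexpensive improvement to a secondary safety outcome, not a flaw that undermines the trial.

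**What to change.** - **Sections 2.7 and 2.8, step 12:** replace the last-progress-note rule with one EMR review per patient after day 7. It should cover all encounter and document types (ED notes, discharge summaries, imaging reports, diagnoses) and any outside records visible in the EMR, and count events by onset date through day 7. Keep the daily inpatient review.
- **Section 2.11:** add the last date on which event status is known, and allow an unknown code for the 7-day outcome.
- **Section 3.1, Aim 2:** report the number per arm with status known to day 7. Show the risk over all randomised patients, and again over those with known 7-day status or an event.
- **Section 3.9:** say that neither denominator removes bias if discharge is related to risk. The first can understate risk. The second can overstate it, because a patient discharged early is counted when an event brings them back but may drop out otherwise. Say also that EMR review cannot see every event treated elsewhere.

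**Cost:** one extra chart look for 48 to 60 patients and two REDCap fields. The reported risk may be higher and its interval wider.
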